**Table 5.1-4: On-Study Assessments for Dose Expansion Phase (Stage 2) (CA212115)**

Procedure	Ulocuplumab administered weekly or every 2 weeks Nivolumab administered every 2 weeks a		Notes
	Week 1, 3, 5, 7, 9, etc ulocuplumab + nivolumab dosing visits	Week 2, 4, 6, 8, 10, etc ulocuplumab dosing visits b	
Safety Assessments			
Targeted Physical Examination	X	X	Within 72 hours prior to dosing
Vital Signs and Oxygen Saturation	X	X	Including BP, HR, respiratory rate, temperature and oxygen saturation by pulse oximetry. Pulse oximetry at rest within 72 hours prior to dosing.
Weight	X		The nivolumab dosing calculations should be based on the body weight. If the subject's weight on the day of dosing differs by > 10% from the weight used to calculate the dose, the dose must be recalculated.
ECOG Status	X		
ECG (12-lead)	See notes		Every 6 weeks from first dose for the first 12 weeks, then every 12 weeks ( $\pm$ 1 wk)
Adverse Events Assessment	Continuous		
Review of Concomitant Medications	X	X	
Laboratory Tests	X	X	Local laboratory assessments should be done within 72 hours prior to each dose through Week 24 and every alternate dose thereafter and include total protein, CBC w/differential, ALT, AST, total bilirubin, direct bilirubin (reflex testing when total bilirubin is elevated), alkaline phosphatase, BUN or serum urea level, uric acid, creatinine, albumin, Ca, Mg, Na, K, P, Cl, LDH, glucose, amylase, lipase, TSH (Free T4 and Free T3 reflex test if TSH result abnormal).

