**Table 5.1-4: On-Study Assessments for Dose Expansion Phase (Stage 2) (CA212115)**

Procedure	Ulocuplumab administered weekly or every 2 weeks Nivolumab administered every 2 weeks a		Notes
	Week 1, 3, 5, 7, 9, etc ulocuplumab + nivolumab dosing visits	Week 2, 4, 6, 8, 10, etc ulocuplumab dosing visits b	
Efficacy Assessment			
Tumor Assessment	See Notes		Every 6 weeks ( $\pm$ 1 wk) from first dose for the first 24 weeks, then every 12 wks ( $\pm$ 1 wk) until disease progression or treatment is discontinued (whichever occurs later). CT chest, CT/MRI abdomen, pelvis and all known sites of disease. Use same imaging method as was used at screening/baseline. Subjects with a history of brain metastasis should have surveillance MRI approximately every 12 weeks, or sooner if clinically indicated
Clinical Drug Supplies			
IVRS call for vial assignment and randomization	X	X	Randomization call will be implemented if a phase 2 randomized study design is initiated
Administer Ulocuplumab treatment (See section 4.5)	X	X	Ulocuplumab will be administered first on days where both therapies are given. For 1600mg every 2 week dosing, ulocuplumab doses will be given Week 1, 3, 5, etc. b
Administer Nivolumab treatment (See section 4.5)	X		If a randomized phase 2 design is initiated for SCLC, the comparator will be nivolumab monotherapy every 2 weeks
Investigator choice chemotherapy treatment	X	X	If a randomized phase 2 design is initiated for PAC, the comparator will be investigator choice chemotherapy

a If a randomized phase 2 design is initiated for SCLC, the comparator will be nivolumab monotherapy following the every 2 week visit schedule (eg, week 1, 3, 5, 7, etc.). If a randomized phase 2 design is initiated for PAC, the comparator will be investigator choice chemotherapy following the weekly visit assessments, as applicable.

b For ulocuplumab every 2 week dosing, ulocuplumab doses will be given Week 1, 3, 5, etc. Visits at Week 2, 4, 6, etc. will not be required.

Table 5.1-5: Follow-up Assessments (CA212115) - All Subjects			
Procedure	Follow Up,a Visits 1 and 2	Survival,b Follow up Visits	Notes
Safety Assessments			
Targeted Physical Examination	X		

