### **8.3.2 Secondary Endpoint(s)**

Safety and tolerability will be analyzed through the incidence of DLTs, adverse events, serious adverse events, and specific laboratory abnormalities (worst grade). Toxicities will be graded using the NCI CTCAE version 4.0.

PFS is defined as the time from first dosing date (randomization date for the randomized Phase 2 study with comparative arm) to the date of the first documented tumor progression, as determined by the investigator (per RECIST 1.1), or death due to any cause, whichever occurs first. Subjects who die without a reported prior progression will be considered to have progressed on the date of their death. Subjects who did not progress or die will be censored on the date of their last evaluable tumor assessment. Subjects who did not have any on-study tumor assessments and did not die will be censored on the date of their first dosing date (randomization date for the randomized Phase 2 study with comparative arm). Subjects who started anti-cancer therapy without a prior reported progression will be censored on the date of their last evaluable tumor assessment prior to the initiation of subsequent anti-cancer therapy.

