#### **8.4.3 Safety Analyses**

Except where indicated, safety analyses will be using the All Treated Subjects population and will be presented as-treated.

During the DLT evaluation Phase, the primary analysis will consist of the incidence of DLTs among DLT-evaluable Subjects but all available safety and tolerability data will be used to assess the safety of the regimens.

For the Dose Evaluation Phase, safety analyses will be summarized by randomized cohort. Additionally, analyses including all safety data collected during that Phase will be provided by regimen.

If the form of the Expansion Phase, is a Simon 2-stage like design, safety analyses will be summarized for the regimen recommended for the Dose Expansion, pooling data from both stages of the study. Additionally, analyses including all safety data collected for that regimen during the Dose Evaluation and the Dose Expansion Phases will be provided.

If a randomized Phase 2 study with comparative arm is initiated, safety analyses will be presented separately by treatment arm.

Events (AEs or laboratory) will be counted as on-study if the event occurred within 100 days of the last dose of ulocuplumab or within 100 days of the last dose of nivolumab, whichever is later. All on-study AEs, treatment-related AEs, SAEs, treatment-related SAEs, AEs leading to discontinuation and treatment-related AEs leading to discontinuation will be tabulated (All Grades and Grade 3-4) using worst grade per NCI CTCAE v 4.0 criteria by system organ class and preferred term. On-study laboratory abnormalities including hematology, chemistry,

liver function, and renal function will be summarized (All Grades and Grade 3-4) using worst grade NCI CTCAE v 4.0 criteria.

[REDACTED]

[REDACTED]

[REDACTED]

[REDACTED]

[REDACTED]

[REDACTED]

[REDACTED]

Baseline and change from baseline in EORTC-QLQ-C30 global health status/QoL composite scale data and the remaining EORTC QLQ-C30 scale data will be summarized by time point using descriptive statistics for each cohort (N, mean, standard deviation, median, first and third quartiles, minimum, maximum). In addition, the percentage of subjects demonstrating a clinically meaningful change (defined as a 10 point change from baseline) will be presented for each scale at each subsequent time point. Percentages will be based on number of subjects assessed at assessment time point.

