 - ◆ If the Dose Expansion Phase is of the form of a Randomized Phase 2 design, a summary of the Dose Expansion Phase will take place, separately from the Randomized data.

- Dose Expansion Phase:
 - 2-stage design
 - ◆ An IA will be conducted when all subjects have a minimum of 3 months of treatment or discontinued prematurely. The objectives of this IA will be similar to item 1) and 2) of the Dose Evaluation Phase IA objectives.
 - ◆ The final analysis will take place when all subjects will have discontinued the study.
 - Randomized Phase 2
 - ◆ IAs will be conducted on a regular basis for the interim monitoring as specified in the Data Monitoring Committee (DMC) charter.
 - ◆ The final analysis will take place when all subjects will have discontinued the study.

At the time of finalizing this SAP, it is known that subjects reported more than 2 DLTs in the “ulocuplumab 400mg weekly combined with nivolumab” cohort (DL1, in PAC subjects). Therefore, and according to protocol, the DL-1 cohort (ulocuplumab 200mg weekly combined with nivolumab) has been initiated. Following this and, considering the current study design, there will be no randomization during the Dose Evaluation phase and no use of the DL3B regimen: “ulocuplumab at 1600mg every 2 weeks combined with nivolumab”. The current version of this SAP is using this information and does not consider that randomization nor the DL3B regimen while describing the planned analyses. Also, as no ulocuplumab dose reduction were reported for the DL1 cohort and as the DL-1 cohort does not allow dose reduction no analysis related to ulocuplumab dose reduction will be planned.

Also, to streamline the document, any reference to the analysis of the potential “Randomized Phase 2” part of the study are not included at this time and may be added at a later time if warranted.

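### In a randomised SCLC Phase 2 with weekly ulocuplumab, the combination arm has twice the scheduled laboratory draws of the nivolumab arm, and the worst-grade tables by arm make no allowance for it

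*Protocol*

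**What the plan says.** Protocol Table 5.1-4 covers the Dose Expansion Phase. It marks laboratory tests in the odd-week column and in the column headed "Week 2, 4, 6, 8, 10, etc ulocuplumab dosing visits". The frequency follows dosing: "Local laboratory assessments should be done within 72 hours prior to each dose through Week 24 and every alternate dose thereafter".

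Footnote a puts the SCLC control on half of those visits: "If a randomized phase 2 design is initiated for SCLC, the comparator will be nivolumab monotherapy following the every 2 week visit schedule". The same footnote puts the PAC chemotherapy comparator on the weekly assessments as applicable, so this exact mismatch is written only for SCLC. Footnote b would remove it if ulocuplumab were given every 2 weeks: "Visits at Week 2, 4, 6, etc. will not be required". However, SAP section 2 says "there will be no randomization during the Dose Evaluation phase and no use of the DL3B regimen". The four regimens in SAP Table 7.4.1-1 (DL-1, DL1, DL2, DL3A) are all weekly.

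Protocol 8.3.2 includes "specific laboratory abnormalities (worst grade") in the secondary safety endpoint. Protocol 8.4.3 tabulates on-study laboratory abnormalities by worst CTCAE grade and adds: "If a randomized Phase 2 study with comparative arm is initiated, safety analyses will be presented separately by treatment arm". Neither section restricts the tables to common visits or adjusts for the number of draws. The SAP leaves analyses of the randomised part to a later version.

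**The concern.** A worst grade is a maximum over the results available for a subject. If one arm is sampled twice as often from the same underlying process, its maximum can only be as high or higher in expectation. A short-lived cytopenia or chemistry abnormality that falls between two control visits is recorded in the combination arm and missed in the control arm.

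The effect falls on a measure that matters here. For the parts it now covers, SAP 7.6.12.1 relies mainly on laboratory data to examine thrombocytopenia, by worst grade and by shift from baseline. Protocol section 7 has the DMC weigh the combination's benefit and risk alongside nivolumab monotherapy. A reader of the tables could attribute to ulocuplumab an excess that comes partly from the sampling schedule.

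**Working it through.** **The plan's own figure.** The documents give no figure for the laboratory comparison. The only computed figure for this part is the ORR power in Protocol 8.1.1: 50 per arm, 35% v 15%, one-sided Fisher exact test at 0.10, about 80%. Exact enumeration gives 80.3%, so it reproduces.

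**Scheduled draws** for a subject who stays on treatment (Table 5.1-4, one draw per dose to Week 24, then every second dose):

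| Through week | Combination | Nivolumab |
|---|---|---|
| 6 | 6 | 3 |
| 12 | 12 | 6 |
| 24 | 24 | 12 |
| 48 | 36 | 18 |

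The Week 1 pre-dose draw is baseline under SAP 6.1, so the post-baseline counts through Week 24 are 24 − 1 = 23 and 12 − 1 = 11.

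**Chance that a scheduled draw catches one episode.** Assume the onset is uniform between draws that are T days apart (T = 7 or 14).
- Fixed duration D: min(1, D/T).
- Exponential duration with mean m: (m/T)(1 − e^(−T/m)).

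| Duration | Weekly | 2-weekly |
|---|---|---|
| Fixed 5 days | 5/7 = 71% | 5/14 = 36% |
| Fixed 7 days | 100% | 7/14 = 50% |
| Fixed 10 days | 100% | 10/14 = 71% |
| Fixed 14 days or more | 100% | 100% |
| Exponential, mean 7 days | 1 − e^(−1) = 63% | 0.5(1 − e^(−2)) = 43% |

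**Apparent incidence.** Assume a true 30% in both arms, one episode per affected subject, and no unscheduled tests.
- Fixed 7 days: 30% v 0.30 × 0.50 = 15%.
- Fixed 10 days: 30% v 0.30 × 0.714 = 21%.
- Exponential, mean 7 days: 0.30 × 0.632 = 19% v 0.30 × 0.432 = 13%.
- Fixed 14 days or more: 30% v 30%.

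If episodes arrive as a Poisson process, so that a subject may have several, the 7-day result is 30.0% v 16.3%.

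**A second model.** Let each draw independently show a Grade ≥ 3 value with the same probability p in both arms. The proportion with at least one is 1 − (1 − p)^k. With k = 24 and 12:
- p = 0.5%: 11.3% v 5.8%.
- p = 2%: 38.4% v 21.5%.
- p = 5%: 70.8% v 46.0%.

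Independence between draws corresponds to very short abnormalities, so this is an unfavourable case. On a common grid k is equal and the expected difference is zero.

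**Scale only.** If someone applied a one-sided Fisher test at 0.10 with 50 per arm and no true difference, it would show an excess in the combination arm with these probabilities at a true 30%:
- 62% for fixed 7-day episodes.
- 24% for exponential durations of mean 7 days.
- About 7% at 14 days or more, which is the level with equal sampling.

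No such test is planned.

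**The case against.** A reader might infer that the whole safety comparison is skewed. The documents do not support that. Table 5.1-4 lists AE assessment as continuous, with no visit marks. Vital signs and examinations also follow the unequal schedule, but 8.4.3 specifies no worst-grade table for them. Tumour assessments run on the same 6-weekly, later 12-weekly, schedule in both arms, so ORR is untouched.

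A reader might also take the 62% as a false-positive rate of the trial. It is not: 8.4.3 describes a presentation by arm, with no test and no alpha. The figure also rests on a fixed 7-day duration, the longest that still gives the full 2:1 ratio. The 5- and 7-day limits in the dosing rules are decision thresholds. They are not evidence of how long abnormalities last.

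Three further points have weight:
- Protocol 5.3 calls for additional laboratory tests as clinically indicated, in either arm. These would catch some events between visits and narrow the gap.
- The randomised part is conditional on at least 9 responders among 19. The binomial probability is 19% at a true rate of 35% and 0.08% at 15%. The SAP defers its analyses openly, and the DMC charter, which is not in the documents, may deal with the matter.
- The bias runs against the combination, so it cannot hide ulocuplumab harm.

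These points limit the size and urgency. They do not remove the problem: Table 5.1-4 and 8.4.3 are current text, and if followed as written they give unequal ascertainment with no correction.

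**Conclusion.** The point holds for laboratory worst-grade tables by arm in a randomised SCLC Phase 2, if it opens with a weekly regimen. The 2:1 ratio of scheduled draws and the direction of the bias follow from the documents. The size does not: it rests on assumed incidence and duration and on scheduled draws alone. For a true 30% in both arms the apparent excess runs from about 15 percentage points (fixed 7-day episodes), through about 6 (exponential, mean 7 days), to none for episodes of 14 days or more. Unscheduled testing would reduce it. The comparison is descriptive, no error rate is affected, and no distortion of ORR or of the AE tables is shown. If a 2-weekly ulocuplumab regimen were reinstated, footnote b would equalise the visits and the point would fall away.

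**What to change.** In Protocol 8.4.3, and in the SAP when the randomised part is added:

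1. Keep the all-results worst-grade and shift tables.
2. Add a by-arm version for the between-arm comparison, restricted to post-baseline scheduled draws at visits common to both arms: Weeks 3, 5, … 23, plus the common follow-up visits.
3. Define any common visits after Week 24 by a window. Sampling at every second dose may not align: if both arms skip Week 25, the weekly arm samples at Weeks 26, 28, 30 and the control at Weeks 27, 31.
4. Report the number of draws per subject by arm, and note on the all-results table that it is affected by unequal sampling.

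No statement about unequal AE elicitation should be added, since AE assessment is continuous in both arms.

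The cost is wording, a visit filter with a window rule, and one extra table. The restricted table undercounts short-lived abnormalities, so it must be read beside the all-results table. Visits and safety monitoring do not change.

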### **5.1.1 Retesting During Screening or Lead-in Period**

Retesting of laboratory parameters and/or other assessments within any single Screening or Lead-in period will be permitted (in addition to any parameters that require a confirmatory value). Any new result will override the previous result (ie, the most current result prior to start of therapy) and is the value by which study inclusion will be assessed, as it represents the subject's most current, clinical state.

## **5.2 Study Materials**

- NCI CTCAE Grading Criteria
- BMS-936564 (ulocuplumab) Investigator Brochure
- BMS-936558 (nivolumab) Investigator Brochure
- Laboratory manuals for collection and handling of blood (including biomarker and immunogenicity) and tissue specimens
- Manual for operation of interactive voice response system
- Manual for entry of local laboratory data
- Pregnancy surveillance forms
- RECIST 1.1 pocket guide
- Questionnaires: EQ-5D, LCSS (for SCLC) and EORTC-QLQ-C30 (for PAC)

## **5.3 Safety Assessments**

Safety assessments should be performed per tables in [Section 5.1](#).

Physical examinations are to be performed per tables in Section 5.1 and as clinically indicated. If there are any new or worsening clinically significant changes since the last exam, report changes on the appropriate non-serious or serious adverse event page.

Women of childbearing potential (WOCBP) must have a negative serum or urine pregnancy test (minimum sensitivity 25 IU/L or equivalent units of HCG) within 24 hours prior to the start of study drug and at time points specified in Section 5.1. Chest X-ray is to be performed for monitoring of pulmonary toxicity per tables in Section 5.1.

Additional measures, including non-study required laboratory tests, should be performed as clinically indicated or to comply with local regulations. Laboratory toxicities (eg, suspected drug induced liver enzyme elevations) will be monitored during the follow-up phase via on site/local labs until all study drug-related toxicities resolve, return to baseline or are deemed irreversible.

Vital signs should be assessed at each on-study visit prior to dosing. Vital signs should also be taken as per institutional standard of care prior to, during and after dosing. Oxygen saturation by pulse oximetry should be obtained prior to dosing and at any time a subject has any new or worsening respiratory symptoms. A reading at rest should be obtained at each time point. If a subject shows changes on pulse oximetry or other pulmonary related signs (eg, hypoxia, fever) or symptoms (eg, dyspnea, cough) consistent with possible pulmonary adverse events, the patient

subject should be immediately evaluated to rule out pulmonary toxicity. An algorithm for the management of suspected pulmonary toxicity can be found in [Appendix 2](#).

Some of the previously referred to assessments may not be captured as data in the eCRF. They are intended to be used as safety monitoring by the treating physician. Additional testing or assessments may be performed as clinically necessary or where required by institutional or local regulations.

### **5.3.1 Imaging Assessment for the Study**

For details on the imaging assessments for response evaluation, refer to [Appendix 3](#).

#### **5.3.1.1 CT/MRI**

Contrast-enhanced Computed Tomography (CT) scans acquired on dedicated CT equipment is preferred for this study. CT with contrast of the chest, abdomen and pelvis are to be performed for tumor assessments every 6 weeks for the first 24 weeks, then every 12 wks until disease progression or treatment is discontinued. CT scans should be acquired with 5mm slices with no intervening gap (contiguous).

Should a subject have a contraindication for CT IV contrast, a non-contrast CT of the chest and a contrast enhanced MRI of the abdomen and pelvis may be obtained. MRI's should be acquired with slice thickness of 5 mm with no gap (contiguous).

Every attempt should be made to image each subject using an identical acquisition protocol on the same scanner for all imaging time points.

- Note: Use of CT component of a PET/CT scanner:

Combined modality scanning such as with FDG-PET/CT is increasingly used in clinical care, and is a modality/technology that is in rapid evolution; therefore, the recommendations outlined here may change rather quickly with time. At present, low dose or attenuation correction CT portions of a combined FDG-PET/CT are of limited use in anatomically based efficacy assessments and it is therefore suggested that they should not be substituted for dedicated diagnostic contrast enhanced CT scans for anatomically based RECIST 1.1 measurements. However, if a site can document that the CT performed as part of a FDG-PET/CT is of identical diagnostic quality to a diagnostic CT (with IV and oral contrast) then the CT portion of the FDG-PET/CT can be used for RECIST 1.1 measurements. Note, however, that the FDG-PET portion of the CT introduces additional data which may bias an investigator if it is not routinely or serially performed

#### **5.3.1.2 MRI Brain**

MRI of brain is required at screening for subjects with SCLC in order to rule out active metastatic disease. Subjects with a history of brain metastasis should have surveillance MRI approximately every 12 weeks, or sooner if clinically indicated.

MRI brain scans during on-study treatment and follow up periods are required only if there is a prior history of lesions present at Screening, or as clinically indicated for new signs and symptoms that suggest central nervous system (CNS) involvement.

Any incidental findings of potential clinical relevance that are not directly associated with the objectives of the protocol should be evaluated and handled by the investigator as per standard medical/clinical judgment.

#### **5.4 Efficacy Assessments**

Study evaluations will take place in accordance with the flow charts in [Section 5.1](#). Baseline tumor assessments should be performed within 28 days prior to the first dose utilizing CT or MRI. In addition to chest, abdomen, pelvis, and brain, all known sites of disease should be assessed at baseline. Subsequent assessments should include chest, abdomen, and pelvis, and all known sites of disease and should use the same imaging method as was used at baseline. Subjects will be evaluated for tumor response beginning 6 weeks ( $\pm 1$  week) from first dose and continuing every 6 weeks ( $\pm 1$  week) for the first 24 weeks and every 12 weeks ( $\pm 1$  week) thereafter, until disease progression is documented or treatment is discontinued (whichever occurs later). Tumor assessments for ongoing study treatment decisions will be completed by the investigator using RECIST 1.1 criteria. For details on the efficacy assessments of overall tumor burden including baseline documentation of “target” and “non-target” lesions and RECIST 1.1 criteria, please see [Appendix 3](#).

